METHODOLOGICAL PROCEDURES & DOCUMENTS MANUAL

Reducing Maternal Depression and Promoting Infant
Social-Emotional Health & Development

NIH R01 HD086894

NCT03464630

Randomized Controlled Trial Design: Prior to iPhone set up, the Intervention Project Coordinator implements randomization procedures. Using a random number generator, mother-infant dyads were randomized, in a 1:1 allocation, to one of the two parallel interventions: Mom and Baby Net or Depression and Developmental Awareness. The Intervention Project Coordinator notifies the PI to review condition assignment and assigns case to intervention coach. (see pages 26 and 98 in Procedures below)

Objective and Specific Aims:

The objective of this project was to address the problem of silo interventions and to improve accessibility to intervention that both reduces maternal depression and improves infant social emotional and communication development. To achieve this objective the following specific aims were addressed:

1. Embed core components of the Mom-Net Internet intervention into the Internet based virtual coaching intervention, Baby Net, to create Mom and Baby Net, an instructionally sound program geared to reduce the internal demands of depressed mothers postpartum.
2. Evaluate the impact of the Mom and Baby Net (MBN) program, as compared to a parallel Internet remote coaching intervention: Depression and Developmental Awareness (DDAS), via a randomized controlled trial. Depressed mothers during the postpartum period and their infants (N=180 dyads) will be randomized to the MBN or DDAS . Impact will be examined relative to:
 - 2.1 Change in parenting behavior, attitudes, beliefs, knowledge, and stress;
 - 2.2 Infant social-emotional behavior and development change;
 - 2.3 maternal depressive symptoms change; and
 - 2.4 Concomitant change in parenting, infant social-emotional, and maternal depressive symptom outcomes as a result of intervention.
3. Evaluate moderating influences on parent and infant behavior within the context of depression during the post partum period. We will focus on:
 - 3.1 The extent to which maternal depression prior to intervention, including current depression symptoms as well as depressive history and chronicity, relate to dosage within the MBN program;
 - 3.2 How dosage moderates parent and infant behavioral change as well as maternal depressive symptom change; and

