(Aims 2.1 - 2.3) Our post-assessment n, to examine acute intervention effects, is expected to be 150 (75/condition). We will initially view intervention effects on our mother/infant outcomes using a 2 (pre-post) $\times 2$ (MBN intervention group) repeated measure analysis of variance. We will examine the inter-correlations among outcomes and, if significant, will use a MANOVA approach to examining MBN intervention effects. The F test is robust to non-normality if such non-normality is caused by skewness rather than outliers. We will take appropriate measures to reduce outlier influences. **(Aim 2.4)** To examine the relations between mother change (parenting and maternal depression) and infant change, one approach will be to create individual beta estimates for mothers and infant utilizing the polynomial contrast function within MANOVA to produce individual trajectory scores reflecting parent and infant change from pre to post that can then be used in external between-condition covariate analysis. The trajectory scores will be subjected to an analysis of covariance with infant change trajectories as the dependent variable and parent change as the covariate. We will determine whether the parent change covariate is significantly related to the dependent variable (demonstrating that changes in parenting behavior and child functioning covary). We will determine the statistical significance and effect sizes of intervention effects (ignoring the covariate). We will then determine if entering the parent functioning covariate modifies the intervention effect size and statistical significance. If parent change is strongly linked to infant change, then entering the covariate should result in nonsignificant intervention effects. Estimates of covariance-adjusted effect sizes will provide estimates of the proportion of intervention effect size that can be explained by the parenting change variable. We will test for between-group heterogeneity of covariance to determine whether the strength of association between change in parenting and infant functioning differs by intervention group.

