
Maintenance of Effects (Aim 4)

Maintenance affects will be viewed by single indicants for maternal and infant functioning. We estimate that our maintenance sample will be at a minimum n=150 (overall 17% attrition). For this aim, we will examine mother-infant change trajectories utilizing SEM methodology, performing Latent Growth Curve Model (LGCM) analyses, and include an Intervention indicant predicting intercept and slope estimates. This analysis will supplement our Aim 2 analyses and, if the index variables within this analysis generally reflect the acute intervention trajectories (*e.g.*, significant intervention acute effects demonstrate with constructs reflect the same differential pre-post index variable trajectory), will allow us to more strongly view the trajectory of change across time. Given the restricted nature of follow-up assessments, balancing participant burden and desire to maximize assessment completion across time, we will view these maintenance trajectories with caution.

Power Analysis

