We expect a pre-post attrition rate of 17% (n=150). For traditional PALS, across a series of randomized control studies, attrition rates ranged from 9% to 24% [26,97]; within our recent Baby-Net R01 study, we evidenced 7% attrition from pre-to- post assessment and 15% at 6-month follow-up working with low-income mothers in KS and OR, some of whom were experiencing elevated levels of depressive symptoms. In this study, a moderate to large effect size ($d=.5 - 1.03$) is anticipated for maternal outcomes and a small to moderate effect size for the infant outcome ($d=.2-.4$ for infants), based on PALS program evidence [18,27], our Baby-Net preliminary results, and evidence of CWDC [100] and Internet-based CBT treatment success [101]. We calculated the smallest effect size to be detected within a 2 x 2 analysis based on .05 alpha, a sample of n=75 per condition and viewed effects relative to a high ($r=.68$) and low ($r=.21$) repeated measures correlation. We found that with power at .95, we could detect an effect as low as $d=.37$ (with low repeated correlation) and $d=.23$ (with high correlation); with power of .80 we could detect an effect size as low as $d=.29$ (with low repeated correlation) and $d=.18$ (with high correlation). Viewing LGCM maintenance trajectories, the number of cases per estimated parameter needs to be sufficient, with a rough guideline of 5:1 [102,103]. Using this guideline, we will have sufficient sample size to estimate 34 parameters within our initial follow-up sample, with 3 time-points and a condition predictor. For our maintenance examination, as noted, we will not statistically view condition differences in trajectories, but rather will hold these examinations to a preliminary view of intervention.

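### The SAP uses one 17% attrition figure (180 to 150) for both post and maintenance, implying no loss after post, and its 34-parameter count matches neither that n nor any lower one

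*SAP*

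**What the plan says.** The Protocol (Objective and Specific Aims, Aim 2) sets the randomised sample: "Depressed mothers during the postpartum period and their infants (N=180 dyads) will be randomized to the MBN or DDAS". Aim 4 places the maintenance assessments at 1, 3 and 6 months after the intervention.

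The SAP then gives three statements about the sample that remains:

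- Examination of Acute Intervention Effects (Aim 2): "Our post-assessment n, to examine acute intervention effects, is expected to be 150 (75/condition".
- Power Analysis: "We expect a pre-post attrition rate of 17% (n=150".
- Maintenance of Effects (Aim 4): "We estimate that our maintenance sample will be at a minimum n=150 (overall 17% attrition".

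As support, the Power Analysis cites earlier PALS trials with attrition of 9% to 24% (time point not given) and the sponsor's Baby-Net study, where "we evidenced 7% attrition from pre-to- post assessment and 15% at 6-month follow-up".

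The same section applies a 5:1 cases-per-parameter guideline to the latent growth curve model. It concludes that 34 parameters can be estimated in the initial follow-up sample, with three time points and a condition predictor. It adds that condition differences in the maintenance trajectories will not be examined statistically and that the analysis is preliminary.

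**The concern.** The same percentage and the same count describe two points in time that are 6 months apart. If 150 is what is expected at post, then 150 at maintenance means that nobody else is lost, and calling it a minimum makes that the worst case. The only study the SAP cites with figures at both times shows attrition roughly doubling over that interval.

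The parameter count raises a second difficulty. It is the only sample-size justification offered for the Aim 4 model, and it does not follow from the n that the SAP gives for that aim.

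At stake are the planning figures for Aim 4: the n a reader should expect behind the 6-month estimates, and the model size that n is said to support. The primary comparison at post is not at issue.

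**Working it through.** **Inputs.** Randomised: 180 (Protocol, Aim 2). Attrition: 17%, used for pre to post and for overall loss (SAP, Power Analysis and Aim 4). Baby-Net attrition: 7% at post and 15% at 6 months (SAP, Power Analysis). Guideline: 5 cases per parameter; stated count: 34 (SAP, Power Analysis).

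**1. Reproduce the SAP's figure.** 180 × (1 − 0.17) = 149.4, rounded to 150. Conversely, 1 − 150/180 = 16.7%. The 150 reproduces, and both the post n and the maintenance n are this one calculation.

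**2. Implied loss after post.** 1 − 150/150 = 0%.

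**3. Baby-Net over the same interval.** Attrition rose by a factor of 15/7 = 2.14. Reading 15% as cumulative from baseline (the natural reading, though not stated), retention from post to 6 months was 0.85/0.93 = 0.914, a further loss of 8.6%.

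**4. What each reading of 150 gives.**

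| Assumption | Post n | 6-month n | Overall attrition |
|---|---|---|---|
| 150 is the post n; Baby-Net retention 0.914 afterwards | 150 | 150 × 0.914 = 137 | 24% |
| 150 is the post n; 15% read as further loss after post | 150 | 150 × 0.85 = 127.5, about 127 | 29% |
| Baby-Net rates applied to 180 throughout | 180 × 0.93 = 167 | 180 × 0.85 = 153 | 15% |

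The third row matters. On Baby-Net's own rates, 150 is an acceptable and slightly cautious 6-month figure, and it is the post figure that departs from the cited experience.

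**5. Parameter count.** 34 × 5 = 170 cases, which is 1 − 170/180 = 5.6% attrition.

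| n | n / 5 | Parameters supported |
|---|---|---|
| 170 | 34.0 | 34 |
| 167 | 33.4 | 33 |
| 153 | 30.6 | 30 |
| 150 | 30.0 | 30 |
| 137 | 27.4 | 27 |
| 127 | 25.4 | 25 |

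The 170 exceeds the stated maintenance n, the expected post n, and even the post n that Baby-Net's 7% would leave.

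**6. Effect on precision.** With observed cases only, standard errors scale with 1/√n. Relative to 150, √(150/137) = 1.046, about 5% wider. At the lower figure, √(1/0.85) = 1.085, about 8% wider.

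**7. Aim 2 power.** This uses 75 per condition at post. Take a 2 × 2 within-between interaction, noncentral F, λ = N·m·f²/(1 − r), with m = 2, d = 2f and N = 150. The detectable d is .372 (r = .21) and .237 (r = .68) at power .95, and .289 and .184 at power .80. The SAP states .37, .23, .29 and .18, so all four agree to within .01. None depends on the maintenance n.

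**The case against.** The strongest reply is that 150 at 6 months is reasonable. The only 6-month attrition the documents cite is 15%, which leaves 153 of 180. On that view 17% is a study-wide planning ceiling, which the word overall permits, and the post figure is deliberately conservative. This stands as far as it goes. It means a reader who infers that the Aim 4 sample is overstated goes further than the documents allow. It does not remove the need for correction, because the SAP presents 150 as the expected post n and rests the Aim 2 power statement on it, without saying that it is a ceiling for the whole study.

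A reader might also scale 17% by 15/7, obtain 36% overall attrition and n = 114, and treat that as a lower bound. Nothing in the documents supports proportional scaling, and 36% exceeds every attrition rate cited (9% to 24% for PALS, 7% and 15% for Baby-Net). At most it is a pessimistic scenario.

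Nor should follow-up be taken as unsupported email. The Protocol's remote post-assessment procedures provide phone reminders and the option of completing the short survey by phone.

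It would also be wrong to say that the parameter count was built on 150 and inherits its error. At 5:1, 34 corresponds to 170, so it disagrees with 150 whatever happens after post.

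Finally, little turns on this. The SAP treats Aim 4 as preliminary. Assume a linear growth curve on one measure, with three time points and one predictor, has about 10 to 12 free parameters. It then needs 50 to 60 cases at 5:1, which every scenario above supplies. A growth model can also use incomplete cases, although the SAP names no missing-data method. This stands and limits the weight of the point. It does not make the printed figures consistent.

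**Conclusion.** The point holds as an inconsistency in the planning figures. One 17% serves as both expected pre-post loss and overall loss, so the implied loss after post is zero, against a rise from 7% to 15% in the sponsor's cited study. Either the post n is conservative or the maintenance minimum is optimistic; the SAP does not say which, and the documents cannot settle it. They therefore do not establish that 150 is too high at 6 months.

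If 150 is the post n, the 6-month n is about 137 with Baby-Net's 15% read as cumulative, or about 127 with it read as further loss. Both rest on Baby-Net's later loss applying here. If 150 is the 6-month n, it agrees closely with Baby-Net's 153 and the post n needs restating.

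The 34 parameters are inconsistent on either reading, since they need 170 cases.

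The consequence is modest: about 5% on standard errors at 137, for an analysis the SAP calls preliminary and for which it plans no statistical comparison of conditions. The Aim 2 power statement stands.

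**What to change.** In the SAP's Aim 4 and Power Analysis sections:

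1. State the expected n separately for post and for follow-up, with an explicit assumption for loss between them, and drop the word minimum.
2. Choose one reading. If 150 remains the post n, give about 137 at 6 months (24% overall), and about 127 as the value if Baby-Net's 15% was further loss after post. If 150 is meant as the 6-month n, say so and restate the post n.
3. State whether Baby-Net's 15% is cumulative from baseline.
4. Replace 34 with the count the chosen n supports: 30 at 150, or 27 at 137.
5. If 114 is shown at all, label it a pessimistic scenario, not a lower bound.

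The cost is a few lines of text and slightly less favourable Aim 4 figures. Enrolment, procedures and the Aim 2 power statement need no change. If the post n is restated upwards, the Aim 2 figures become somewhat conservative.

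### The SAP's minimum detectable effects are half what the group × time test needs, so stated 80% power is really about 29%

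*SAP*

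**What the plan says.** The SAP section on acute intervention effects (Aim 2) plans a two-by-two analysis, pre-post by "MBN intervention group) repeated measure analysis of variance". The number analysed "is expected to be 150 (75/condition"), after 17% attrition from the 180 dyads in the Protocol's specific aims.

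The Power Analysis section describes its calculation this way: "We calculated the smallest effect size to be detected within a 2 x 2 analysis based on .05 alpha, a sample of n=75 per condition". It takes a high (.68) and a low (.21) pre-post correlation and reports that "with power of .80 we could detect an effect size as low as $d=.29$ (with low repeated correlation) and $d=.18$ (with high correlation"). At 95% power the corresponding values are .37 and .23.

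The same paragraph anticipates d of .5 to 1.03 for maternal outcomes and "a small to moderate effect size for the infant outcome ($d=.2-.4$ for infants"). It does not define d, and it does not say which term of the two-by-two was powered.

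**The concern.** The detectable effects look too small for 75 per arm. A comparison of post-test means alone, at that size and two-sided .05, needs d=.46 for 80% power. At r=.21 a pre-post change score is noisier than the post-test score, because its variance is 2(1−.21)=1.58 against 1. An analysis of change at that correlation must therefore need more than .46, yet the SAP says .29.

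The calculation exists to be read against the anticipated effects. If the detectable values are half their true size, the plan appears to cover most of the infant range when it does not. Infant social-emotional change is a named aim (Aim 2.2). With low true power, a non-significant infant result would say little about whether the intervention works, and the SAP as written would not warn the reader of that.

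**Working it through.** **Inputs.** Alpha .05, 75 per arm (N=150), r=.21 and .68, and power .80 and .95 come from the SAP's Power Analysis. The 2 × 2 repeated-measures ANOVA comes from the SAP's Aim 2 section. Sidedness is not stated, so the ordinary 1-df F test (two-sided) is assumed.

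**Step 1: reproduce the SAP's figures.** For a within-subject or group × time term with m=2 waves, the F test has 1 and 148 df and noncentrality

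λ = f² · N · m / (1−r) = f² · 300 / (1−r).

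Solve for f, then double it:

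| Power | r | f | 2f | SAP |
|---|---|---|---|---|
| .80 | .21 | .1447 | .289 | .29 |
| .80 | .68 | .0921 | .184 | .18 |
| .95 | .21 | .1862 | .372 | .37 |
| .95 | .68 | .1185 | .237 | .23 |

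Check: .1447² × 300/.79 = 7.95, the λ for 80% power. Likewise .1862² × 300/.79 = 13.17 for 95%. If d is read as 2f, power at the four stated values is 80.2%, 78.2%, 94.8% and 93.8%. The figures reproduce, apart from .237 being given as .23.

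**Step 2: what 2f measures.** For the time main effect, the pre and post means sit at −f and +f (in SD units), so the pooled change is 2f. For the interaction, the cells deviate by +f (MBN post), −f (MBN pre), −f (DDAS post) and +f (DDAS pre). The between-arm difference in change is

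[f − (−f)] − [(−f) − f] = 4f.

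The intervention effect is that second quantity.

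**Step 3: the detectable intervention effect.** The group × time test is a two-sample comparison of change scores with SD √(2(1−r)), so

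MDE = √λ · √(2(1−r)) · √(2/75).

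| Power | r | Calculation | Detectable d | SAP |
|---|---|---|---|---|
| .80 | .21 | 2.820 × 1.257 × .1633 | .58 | .29 |
| .80 | .68 | 2.820 × .800 × .1633 | .37 | .18 |
| .95 | .21 | 3.628 × 1.257 × .1633 | .74 | .37 |
| .95 | .68 | 3.628 × .800 × .1633 | .47 | .23 |

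These equal 4f from Step 1 (.579, .368, .745, .474). Replacing √(2/75) by 1/√150 gives the pooled change over all 150 mothers: .289, .184, .372 and .237, which are the SAP's figures.

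**Step 4: true power at the stated values.** With d=4f, λ = (d/4)² · 300/(1−r). For d=.29 and r=.21 this is .0725² × 300/.79 = 2.0, a quarter of what is needed, and power is 29%. For d=.18 and r=.68 it is 28%. For the pair stated at 95%, power is 43% and 42%. A simulation of 20,000 trials per setting gave 29% and 28% at the SAP's 80%-power values, and 80% at both d=.58 (r=.21) and d=.37 (r=.68).

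**Step 5: power over the anticipated effects.**

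| Outcome | d | r=.21 | r=.68 |
|---|---|---|---|
| Infant | .2 | 16% | 33% |
| Infant | .3 | 31% | 63% |
| Infant | .4 | 49% | 86% |
| Maternal | .5 | 68% | 97% |
| Maternal | .6 | 83% | >99% |
| Maternal | 1.03 | >99% | >99% |

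**Step 6: could another reading give .29 and .18 as a group effect?** The 80%-power values for r=.21 / .68 are:

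- one-sided group × time: .51 / .33
- between-subject main effect: .36 / .42, which rises with r while the SAP's values fall
- change-score SD units: .46 / .46
- baseline-adjusted (ANCOVA): .4605 × √(1−r²) = .45 / .34

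None matches.

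**The case against.** The strongest reply is that the SAP never defines d or names the term it powered. Doubling f is therefore a reconstruction, and powering the time term would give the same numbers. If d simply means 2f, the four figures are internally correct. This is fair as to cause, but it does not rescue the section. The anticipated effects are drawn from earlier program and treatment evidence, and setting detectable values beside them requires a common scale. If d is 2f, the section does not show power for those effects; if d is the usual between-arm difference, the values are half what they should be.

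Several limits do stand.

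- The documents do not say how the anticipated d values were standardised, so the percentages in Step 5 assume they are between-arm differences in outcome-SD units.
- The SAP draws no explicit conclusion that the sample is adequate for these outcomes; the juxtaposition implies it. Nor does it set a rule for reading a null infant result.
- The shortfall is not uniform. Maternal power stays above 80% over most of the range, and infant d=.4 at r=.68 is adequate.
- Part of the infant shortfall was already visible: d=.2 lies below the SAP's own .29 at r=.21, with 49% power even on the 2f scale.
- If the outcomes inter-correlate and the SAP moves to MANOVA, univariate figures do not describe that test.

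**Conclusion.** The concern holds. All four detectable effects are half the size required for the group × time test that the SAP plans; the factor is exactly 2 before rounding. The correct values are d=.58 and .37 at 80% power and .74 and .47 at 95%, for r=.21 and .68. At r=.21 no anticipated infant effect reaches 50% power. At r=.68, 80% power begins at d=.37, near the top of the infant range.

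This rests on 75 analysed per arm, two-sided .05, equal variances at the two waves, and d defined as the between-arm difference in pre-post change in outcome-SD units. That definition equals the post-test difference when baselines are equal. A one-sided test would not restore the stated figures.

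**What to change.** In the SAP's Power Analysis:

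- Define d as the between-arm difference in pre-post change divided by the outcome SD, and name group × time as the term powered.
- Replace the detectable effects with .74 / .47 (95% power) and .58 / .37 (80% power) for r=.21 / .68.
- State that power for the infant outcome is about 16% to 86% over d=.2 to .4, and that a non-significant infant result is therefore inconclusive.
- State the sidedness of the test, and note that the figures apply to the univariate analysis.

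If the SAP's primary analysis were changed to a baseline-adjusted comparison, the 80%-power values to quote would be .45 / .34. That would still not reach d=.2.

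The cost is SAP wording only. The stated figures become less favourable; enrolment and procedures do not change.

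### The SAP's 5:1 rule supports 30 growth-model parameters at the planned follow-up sample of 150, not the 34 stated; the practical effect is small.

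*SAP*

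**What the plan says.** The Power Analysis section of the SAP sets the rule for the growth models: "the number of cases per estimated parameter needs to be sufficient, with a rough guideline of 5:1". Applying it, the section says "we will have sufficient sample size to estimate 34 parameters within our initial follow-up sample", for a model with three time-points and a condition predictor.

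The sample sizes are given in several places:

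- Protocol, Objective and Specific Aims (Aim 2): "Depressed mothers during the postpartum period and their infants (N=180 dyads) will be randomized".
- SAP, Examination of Acute Intervention Effects (Aim 2): 150 at post-assessment, 75 per condition.
- SAP, Maintenance of Effects (Aim 4): "We estimate that our maintenance sample will be at a minimum n=150 (overall 17% attrition").
- SAP, Power Analysis: "We expect a pre-post attrition rate of 17% (n=150").

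The Power Analysis also cites earlier experience: 9% to 24% attrition across previous PALS trials, and for the Baby-Net study "we evidenced 7% attrition from pre-to- post assessment and 15% at 6-month follow-up".

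The SAP does not list the parameters of the growth model. The Aim 4 section says that single measures will be used for mother and infant, with condition predicting intercept and slope, and that the results will be read cautiously.

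**The concern.** The figure of 34 is presented as the result of applying the 5:1 rule to the follow-up sample, so a reader should be able to recover it from the planned sample size. That is not possible: every sample size that the SAP plans for after baseline is 150.

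This matters because the parameter count is the only sample-size support given for the Aim 4 growth models. The detectable effects in the same section are for the 2 × 2 analysis at 75 per condition. An analyst who took 34 as the permitted model size could specify a model that looks compliant and yet falls short of the SAP's own ratio.

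**Working it through.** **Inputs.** Rule: 5 cases per parameter (SAP, Power Analysis). Stated capacity: 34 parameters (same section). Planned sample: 150 at post-assessment and at least 150 for maintenance (SAP, Aim 2, Aim 4 and Power Analysis sections). Randomized: 180 dyads (Protocol, Aim 2).

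**Formulas.** Capacity = n / 5, rounded down. Cases needed = 5 × parameters.

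**Step 1: try to reproduce 34.** A whole-number capacity of 34 needs between 34 × 5 = 170 and 35 × 5 − 1 = 174 cases. The sample sizes that the documents could support are:

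| Basis | n | n / 5 | Whole parameters |
|---|---|---|---|
| Planned post-assessment and maintenance sample | 150 | 30.0 | 30 |
| 180 less 17% (planned rate) | 149.4 | 29.9 | 29 |
| 180, no loss | 180 | 36.0 | 36 |
| 180 less 7% (Baby-Net, pre-post) | 167.4 | 33.5 | 33 |
| 180 less 15% (Baby-Net, 6 months) | 153 | 30.6 | 30 |
| 180 less 9% (PALS, low end) | 163.8 | 32.8 | 32 |
| 180 less 24% (PALS, high end) | 136.8 | 27.4 | 27 |

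None gives 34. The nearest is the 7% row. That is another study's pre-post rate, which this SAP does not adopt, and it still yields only 33 whole parameters.

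**Step 2: size of the discrepancy.**

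- Shortfall in cases: 170 − 150 = 20.
- Overstatement of capacity: 34 / 30 = 1.13, or 13%.
- Ratio at 34 parameters: 150 / 34 = 4.41 cases per parameter.
- Attrition that would leave 170 of 180: 1 − 170/180 = 5.6%, against 17% planned and below every rate that the SAP cites.
- Number to randomize to retain 170 after 17% loss: 170 / 0.83 = 204.8, so 205.

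**Step 3: does any likely model come near the limit?** The SAP gives no specification, so the following counts rest on an assumed linear growth model with three time-points and a condition predictor.

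- One outcome: 2 growth-factor intercepts + 2 variances + 1 covariance + 3 residual variances + 2 condition paths = 10 parameters. Three measurements plus condition are 4 variables, which supply 10 variances and covariances + 4 means = 14 observed moments. A 34-parameter model could not be identified.
- Parallel mother and infant outcomes: 4 intercepts + 4 variances + 6 covariances + 6 residual variances + 4 condition paths = 24. Adding 3 cross-outcome residual covariances gives 27, and counting the mean and variance of condition gives 29. Seven variables supply 28 + 7 = 35 observed moments, so a 34-parameter model would be almost saturated.

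All of these counts lie within 30.

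**The case against.** The best defence has four parts.

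First, 150 is called a minimum, so a larger follow-up sample is not ruled out. That is so, but the post-assessment sample that precedes follow-up is also planned at 150, and nothing in the plan supports 170.

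Second, the SAP's Random Sampling/Attrition Analysis section adopts an intent-to-treat approach that includes everyone recruited. If that governs Aim 4, 180 / 5 = 36 covers 34. This makes it too strong to say that the design cannot support 34 parameters. It does not rescue the sentence, which ties the claim to the follow-up sample, and 36 is not 34 either.

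Third, 34 is a capacity and not a proposed model, and Step 3 shows that likely models do not approach it. This stands and limits the consequence.

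Fourth, the rule is called rough, Aim 4 is to be read with caution, and the Power Analysis says that condition differences in trajectories will not be tested. This also stands. It lowers the weight of the error without making the figure correct.

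A reader might go further and carry Baby-Net's additional loss between post-assessment and six months over to this trial, arriving at a limit below 30. The documents do not support that. The Aim 4 section gives 17% as the overall attrition and 150 as the minimum, and the sentence at issue concerns the initial follow-up sample.

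**Conclusion.** The stated capacity does not follow from the SAP's own rule and planned sample. At n=150 the 5:1 guideline supports 30 parameters; 34 would need 170 cases. This rests only on figures in the documents.

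The practical effect is small. The finding that plausible models fit within 30 depends on the linear specification assumed in Step 3, because the SAP gives none. A reader might infer that the Aim 4 model will break the 5:1 rule or that the trial is too small for it. Neither follows: the SAP describes no model of that size, and it holds Aim 4 to a preliminary view. The documents also do not show whether 34 is a slip or reflects an unstated follow-up sample size.

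**What to change.** In the SAP's Power Analysis, either restate the capacity as 30 parameters at n=150, or state the initial follow-up sample size and attrition that give 34 and reconcile them with the minimum of 150 and 17% overall attrition in the Aim 4 section. Keep any Aim 4 growth model within the resulting number.

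The cost is one corrected figure or one added sentence. Recruitment, assessments and the number randomized are unaffected.
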